### 3.2 Definition of Study Periods

The **Screening Period** will begin once a patient has signed the consent form and concludes with either a screen failure decision or initiation of study dosing on Rollover C1D1 (RC1D1). During the Screening

Period, patients are evaluated against the study inclusion and exclusion criteria (see [Section 5](#) Population Selection Criteria). The screening window for all procedures will be up to 21 days. Please note, if the last dose of IMCgp100 on the parent study and the first dose of IMCgp100 on the rollover study are separated by more than 21 days, the first dose of IMCgp100 must be administered with overnight inpatient monitoring; given the risk of severe infusion-related toxicity and potential for hypotension (refer to [Section 1.4](#) for details of clinical experience with IMCgp100).

The **Treatment Period** will begin with the first treatment in the first cycle with RC1D1. For the purpose of treatment scheduling, a cycle consists of 4 weeks. The Treatment Period consists of the time from RC1D1 until the end of study treatment.

The **90-day Safety Follow-up Period** consists of the time from the last dose of study medication for a period of 90 days. Safety observations during this 90-day Follow-up Period are outlined in [Section 7.2.3](#) and include reporting of all AEs and all serious AEs (SAEs) in the same manner as the Treatment Period.

The **Survival Follow-up Period** will initiate after the 90-day Follow-up Period and continue until death. As applicable, all patients will be followed for survival until the end of the study is reached.

### 3.3 Definition of End of Treatment

In all patients in this study, IMCgp100 will be administered IV according to the defined regimen. Patients will continue to receive IMCgp100 until loss of clinical benefit for the individual patient (as per local imaging standard of care and the appropriate response criteria, as defined by the principal investigator), unacceptable toxicity as defined by the principal investigator or Sponsor, withdrawal of consent, loss to follow-up, or death.

### 3.4 Definition of End of Study

The end of the study will be when all patients enrolled have completed IMCgp100 treatment or the study is terminated by the Sponsor.

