### 3.5 Early Study Termination

The study can be terminated at any time for any reason by the Sponsor. Should this be necessary, any ongoing patient should be seen as soon as possible for end of treatment (EOT) visit and the assessments should be performed as described in [Table 7-1](#).

The investigator may be informed of additional procedures to be followed in order to ensure that adequate consideration is given to the protection of the patient's interests. Under guidance of the Sponsor, the investigator will be responsible for informing the Institutional Review Board (IRB) and Independent Ethics Committee (IEC) of the termination of the trial.

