### 7.2.2 Discontinuation of Study Treatment

Patients may voluntarily discontinue from the study treatment for any reason at any time. If a patient decides to discontinue from the study treatment, the investigator should make every effort to determine the primary reason for this decision and record this information in the patient's chart and

on the appropriate eCRF pages. Other reasons for discontinuation of study treatment are outlined in [Section 6.6](#).

Patients will be considered withdrawn from treatment if they state an intention to withdraw, fail to return for visits, or become lost to follow-up for any other reason.

The investigator should discontinue study treatment for a given patient if he/she believes that continuation would be detrimental to the patient's well-being.

At the time patients discontinue study treatment, a visit should be scheduled as soon as possible, within 14 days of the last dose of study drug or within 14 days of the decision to permanently discontinue study treatment, at which time all of the assessments listed for the EOT visit will be performed ([Table 7-1](#)). If the decision to withdraw the patient occurs at a regularly scheduled visit, that visit may become the EOT visit rather than having the patient return for an additional visit. An end of treatment eCRF page should be completed, giving the date and reason for stopping the study treatment. End of treatment/premature withdrawal visit is not considered as the end of the study.

Patients who discontinue study treatment should NOT be considered withdrawn from the study. They should return for the assessments indicated in [Section 7](#) and [Table 7-1](#) and be followed for the 90-day Safety Follow-up Period at a minimum. If they fail to return for these assessments for unknown reasons, every effort (eg, telephone, email, postal letter) should be made to contact them. At this time, the reason for study completion should be recorded on the Study Disposition eCRF page.

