### 7.2.3 90-day Safety Follow-up Period

All patients must have safety evaluations 90 days after the last dose of study treatment. Information related to all AEs (including concomitant medication taken for ongoing AEs) will be collected for 90 days after the last dose of study drug. All AEs suspected to be related to study treatment should be followed up weekly or as clinically indicated until resolution or stabilization.

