### 7.2.4 Survival Follow-up Period

Upon completion of the 90-day follow-up, patients will be followed for survival every 3 months (can be done by telephone call) until death or until the end of the study is reached, unless they withdraw consent or are lost to follow-up.

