15.1. Adverse Events

Patients with multiple adverse events in the same category are counted only once in that category and those with adverse events in more than 1 category are counted once in each of those categories. Adverse Events (AEs) will be coded using Medical Dictionary for Regulatory Activities (MedDRA) central coding dictionary, using the latest version of MedDRA available at the time of coding for the reporting period.

Treatment-emergent adverse events (TEAEs) are defined as AEs that started or worsened in severity from the date of first dose of the rollover study (regardless of time) up until 90 days after the last dose of study drug of this rollover study.

See [APPENDIX 2](#) for handling of partial dates for AEs. In the case where it is not possible to define an AE as treatment-emergent or not, the AE will be classified by the worst case; i.e. treatment emergent.

An overall summary of number of patients within each of the categories described in the subsection below, will be provided as specified in the templates.

An AE Listing will include TEAEs and Non-TEAEs, including those from before the first dose in the parent study and post-treatment periods which will be flagged as such. Only TEAEs will be summarized.

AE Structure as Recorded in the eCRF:

AEs will be recorded in the eCRF such that any change in severity over the course of their duration will be recorded as a single record. The AE/SAE eCRF page collects ‘Initial Grade’ and ‘Most Extreme Grade’ but not the date of the severity grade change. No further manipulation post collection is required, and the AE/SAE data will be listed as recorded.

The definition of a treatment-emergent AE will be handled for AEs that change in severity over the course of their duration, by assuming that any AE that *might have worsened* in severity within the timeframe from the date of first dose of the rollover study (regardless of time) up until 90 days after the last dose of study drug, will be defined as treatment-emergent. A worsening severity is defined as changing from a less severe (lower) CTCAE grade to a more severe (higher) CTCAE grade. For example, if an AE started prior to date of first dose of the parent study but ended on or after date of first dose of the parent study (regardless of time), and the ‘Most Extreme Grade’ is more severe (higher) than the ‘Initial Grade’, then the AE is assumed to be treatment-emergent.

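### Protocol 3.4 ends the study when the last patient finishes treatment, which conflicts with the mandatory 90-day safety follow-up and the SAP's adverse-event window

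*Protocol*

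**What the plan says.** Protocol 3.4 fixes when the study closes: "The end of the study will be when all patients enrolled have completed IMCgp100 treatment or the study is terminated by the Sponsor".

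Protocol 3.2 defines separate, consecutive periods. On treatment: "The Treatment Period consists of the time from RC1D1 until the end of study treatment". The 90-day Safety Follow-up Period then "consists of the time from the last dose of study medication for a period of 90 days", and the Survival Follow-up Period starts after that.

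The 90-day duty is repeated without reference to the end of study. Protocol 7.2.3: "All patients must have safety evaluations 90 days after the last dose of study treatment". Protocol 7.2.2 says that patients who stop treatment should "be followed for the 90-day Safety Follow-up Period at a minimum". Protocol 6.5, 8.1 and 8.5 set the same 90 days for AEs, SAEs or both.

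Survival follow-up is tied to the end of study. Under Protocol 7.2.4 it runs "until death or until the end of the study is reached", and 3.2 says the same in other words.

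On Sponsor termination, Protocol 3.5 says that "any ongoing patient should be seen as soon as possible for end of treatment (EOT) visit", with assessments as in Table 7-1. It does not say whether 90-day collection follows.

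SAP 15.1 counts treatment-emergent AEs from the first rollover dose "up until 90 days after the last dose of study drug of this rollover study". SAP 4 and 4.1 plan one final analysis after database lock and do not link the lock to completion of the 90 days.

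**The concern.** AE incidence is the primary endpoint, and the SAP summarises it over a window that closes 90 days after the last dose. Read literally, Section 3.4 closes the study at the start of the last patient's 90 days. Two sets of instructions then apply to the same patients: the study is over, and safety data must still be collected. A site, a monitor or a data manager could act on either.

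If the study closes or the database locks on the 3.4 date, late AEs in the last patients to stop would be missing from the primary summary, and no rule in either document would have been broken. Survival contact would stop for everyone on that date, although OS is a secondary objective in Protocol 4.2.

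**Working it through.** The documents give no sample size, event count or other figure to reproduce on this point. The check is timeline arithmetic.

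**Inputs**
- End of study E: the date on which the last patient completes treatment (Protocol 3.4), taken here as that patient's last dose.
- Post-dose AE window: 90 days (Protocol 3.2, 7.2.3 and 8.5; SAP 15.1).
- Survival follow-up: starts after day 90 (Protocol 3.2) and stops at E (Protocol 3.2 and 7.2.4).

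**Formulas**, for a patient whose last dose is t days before E:
- post-dose days inside the study = min(90, t)
- post-dose days outside = 90 − min(90, t)
- survival follow-up days = max(0, t − 90)

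| t (days) | Inside | Outside | Share outside | Survival follow-up (days) |
|---|---|---|---|---|
| 0 | 0 | 90 | 100% | 0 |
| 7 | 7 | 83 | 92% | 0 |
| 14 | 14 | 76 | 84% | 0 |
| 30 | 30 | 60 | 67% | 0 |
| 60 | 60 | 30 | 33% | 0 |
| 90 | 90 | 0 | 0% | 0 |
| 180 | 90 | 0 | 0% | 90 |

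The conflict reaches every patient whose last dose falls within 90 days before E, not only the last one. The shares refer to the 90-day tail alone; AEs from first to last rollover dose are unaffected.

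**Other reading of 3.4.** If completing treatment means attending the EOT visit, and that visit falls on day 14, the last patient sits in the t = 14 row. The conflict remains.

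**Sponsor termination.** E is then the termination date. Assuming weekly dosing on schedule with no hold, an ongoing patient has t of 0 to about 7, so 83 to 90 of the 90 days fall after E. This would apply to all ongoing patients at once.

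**After the fix.** Suppose the last patient completes 90 days and E moves to E + 90. Every patient then has t + 90 ≥ 90 days available, so the full window fits. Survival follow-up becomes max(0, t + 90 − 90) = t days, which is still 0 for the last-treated patient.

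**The case against.** The strongest reply is that nothing need be lost. The 90-day collection is mandatory, is stated in several sections, and is never made conditional on the end of study; only survival follow-up is. Protocol 7.2.2 says that stopping treatment is not withdrawal from the study. SAP 17 lists a day-90 safety follow-up CRF page, so the visit was built into data capture. The SAP ties the final analysis to database lock, not to the 3.4 date. All of this stands, and it rules out a claim of certain data loss. It does not remove the contradiction: a site that follows 7.2.3 is working in a study that 3.4 says has ended, and no text makes the lock wait.

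Protocol 6.6 and 7.2.2 add that the EOT visit is not the end of the study. That concerns the individual patient's visit and does not amend 3.4.

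On Section 3.5, the sentence goes on to cite Table 7-1, which has 90-day and survival columns, and 3.5 allows for additional procedures. It never limits follow-up to the EOT visit. The gap is that continuation is left unstated.

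A reader might infer more than the documents support on three matters:
- That Sponsor termination leaves at most 14 of 90 days. Protocol 7.2.2 also allows the EOT visit within 14 days of the decision to discontinue, so after a dose hold it can fall later than day 14. The visit is also not stated to end AE collection.
- That OS is censored at last treatment. SAP 14.1 censors at the last date known alive, drawn from many eCRF pages, so data from the 90-day follow-up would move that date later.
- That the affected patients are those with the longest exposure. The last to stop need not have been treated longest; that depends on entry dates and parent-study exposure, which the documents do not give.

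Finally, stopping survival follow-up when a continued-access study ends is ordinary administrative censoring. There is no hypothesis test, Protocol 9.7.1 places OS under exploratory analyses, and Kaplan-Meier handles such censoring. This also stands: the cost is follow-up time and deaths not captured, not a wrong method.

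**Conclusion.** The conflict is real and should be reconciled. As written, 3.4 places up to 90 of 90 post-dose days outside the study for any patient whose last dose falls within 90 days of the end date, and gives those patients no survival follow-up period. The two parts differ in strength. Survival follow-up is stopped by the protocol's own words. The AE window is subject to contradictory instructions, so its data are at risk but not necessarily lost.

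The arithmetic takes completion of treatment as the last dose. The number of patients affected cannot be computed, because no enrolment figure is given. How many AEs would be missed depends on when closure and lock occur in practice, which the documents do not say.

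**What to change.** 1. Protocol 3.4: define end of study as no earlier than the date on which the last patient completes the 90-day Safety Follow-up, or has died, withdrawn or been lost to follow-up. This reconciles it with 7.2.3.
2. Protocol 3.5: state that 90-day AE and SAE collection still applies after Sponsor termination, in addition to the EOT visit.
3. SAP 4.1: tie database lock to the date in item 1.

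Survival is a separate design decision. Item 1 alone still leaves the last-treated patient with no survival follow-up period. The sponsor can either name a survival cut-off or say plainly that survival contact ends with the study.

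The cost is about one sentence in each of the three places. Study closure moves about 3 months (90 days) later than 3.4 implies, but Protocol 7.2.3 and 8.5 already require that follow-up, so no new patient assessment is added.

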### 3.5 Early Study Termination

The study can be terminated at any time for any reason by the Sponsor. Should this be necessary, any ongoing patient should be seen as soon as possible for end of treatment (EOT) visit and the assessments should be performed as described in [Table 7-1](#).

The investigator may be informed of additional procedures to be followed in order to ensure that adequate consideration is given to the protection of the patient's interests. Under guidance of the Sponsor, the investigator will be responsible for informing the Institutional Review Board (IRB) and Independent Ethics Committee (IEC) of the termination of the trial.

## 4 STUDY OBJECTIVES AND ENDPOINTS

### 4.1 Primary Objective

The primary objective is to determine the number of patients with AEs associated with IMCgp100 treatment.

### 4.2 Secondary Objectives

- To characterize the long-term safety (> 1 year dosing) and tolerability profile associated with treatment with IMCgp100
- To evaluate the incidence of anti-IMCgp100 antibody formation following multiple infusions of IMCgp100
- To estimate the OS of patients treated with IMCgp100

### 4.3 Primary Endpoint

The primary endpoint is incidence of AEs associated with IMCgp100.

### 4.4 Secondary Endpoints

- Tolerability: Dose interruptions, reductions, and dose intensity of IMCgp100
- Assessments of anti-IMCgp100 antibody formation
- Date of death in all patients treated with IMCgp100

**Table 4-1 Objectives and Related Endpoints**

Objective(s)	Endpoint(s)
Primary	
To determine the number of patients with adverse events associated with IMCgp100 treatment	Incidence of adverse events
Secondary	
To characterize the long-term safety (> 1 year dosing) and tolerability of IMCgp100	Tolerability: Dose interruptions, reductions, and dose intensity of IMCgp100

**Table 4-1 Objectives and Related Endpoints**

Objective(s)	Endpoint(s)
To evaluate the incidence of anti-IMCgp100 antibody formation following multiple infusions of IMCgp100	Assessments of anti-IMCgp100 antibody formation
To estimate the overall survival in patients treated with IMCgp100	Date of death in all patients treated with IMCgp100

## 5 POPULATION SELECTION CRITERIA

### 5.1 Patient Population

This rollover study will enroll patients who have been treated as part of an IMCgp100 clinical study that has completed. At the time of rollover study entry, patients must be continuing to receive IMCgp100 as part of the active parent study and for whom the study is completing. Patients must not have any ongoing, serious IMCgp100-related toxicities at the time of rollover study entry that would preclude further dosing in the opinion of the investigator or the Sponsor.

### 5.2 Inclusion Criteria

Patients eligible for inclusion in this study must meet **all** of the following criteria:

1. Patient is currently participating in an Immunocore-sponsored study of IMCgp100 and is actively receiving IMCgp100. Patient must have fulfilled all required assessments in the parent study (unless the study is being terminated)
2. Patient is currently receiving clinical benefit from the treatment with IMCgp100, as determined by the principal investigator from the parent study
3. Patient has demonstrated compliance with the parent study requirements, as assessed by the principal investigator and patient is able to comply with the necessary visits and assessments as part of the rollover study
4. Written informed consent must be obtained prior to enrolling in the rollover study and receiving the study treatment. If consent cannot be expressed in writing, then the consent must be formally documented and witnessed, ideally via an independent trusted witness

### 5.3 Exclusion Criteria

Patients eligible for this study must not meet any of the following criteria:

1. Patient has been permanently discontinued from any IMCgp100 study or from IMCgp100 treatment in the parent study due to unequivocal PD, unacceptable toxicity, non-compliance to study procedures, withdrawal of consent, or any other reason
2. Pregnant or nursing (lactating) women, where pregnancy is defined as the state of a female after conception and until the termination of gestation, confirmed by a positive human chorionic gonadotropin laboratory test

3. Women of child-bearing potential who are sexually active with a non-sterilized male partner, defined as all women physiologically capable of becoming pregnant, unless they are using 2 methods of highly effective contraception from Screening, and must agree to continue using such precautions for 6 months after the final dose of investigational product; cessation of birth control after this point should be discussed with a responsible physician. Highly effective methods include barrier methods, intrauterine devices or hormonal methods. Periodic abstinence, the rhythm method, and the withdrawal method are not acceptable methods of birth control. Women of child-bearing potential must have a negative serum pregnancy test at Screening. Otherwise, female patients must be post-menopausal (no menstrual period for at least 12 months prior to Screening), or surgically sterile
  
4. Male patients who are not surgically sterile unless they are using a double barrier contraception method from enrollment through treatment and for 6 months following administration of the last dose of study drug

## 6 STUDY TREATMENTS AND ADMINISTRATION

### 6.1 Study Treatment

For this study, the investigational drug refers to IMCgp100. Study drug will be supplied by the Sponsor, Immunocore.

All dosages prescribed and dispensed to patients and all dose changes during the study must be recorded on the Dosage Administration Record electronic case report form (eCRF).

**Table 6-1 Dose and Treatment Schedule**

Study Treatment	Pharmaceutical Form and Route of Administration	Dose	Frequency and/or Regimen
IMCgp100	[REDACTED]	[REDACTED]	Weekly

For all study medication administration, a physician must be present at the site or immediately available to respond to emergencies during all administrations of all study medications. Fully functional resuscitation facilities should be available. [REDACTED]

[REDACTED]

[REDACTED]

[REDACTED]

[REDACTED]

[REDACTED]

## 6.2 Concomitant Therapy

### 6.2.1 Permitted Concomitant Therapy

Concomitant medications and therapies deemed necessary for the supportive care and safety of the patient are allowed in general. Examples include anti-diarrheal medications, anti-emetics, or electrolyte supplementation.

Patients must be told to notify the investigational site staff about any new medications, herbal remedies, or dietary supplements that he or she takes after the start of the study treatment, regardless of treatment duration. All concomitant medications and significant non-drug therapies (including physical therapy, herbal or natural medications, and blood transfusions) administered during the study must be listed on the Concomitant Medications or other relevant eCRF.

IV hydration required to manage toxicity associated with any of the study treatments (eg, hypotension) should be recorded in the Concomitant Medications eCRF. IV hydration prior to administration of study treatments does not need to be recorded in the eCRF unless fluids are prescribed to manage toxicity.

### 6.2.2 Permitted Concomitant Therapy Requiring Caution

Anti-coagulant therapy is permitted if the patients are already at stable doses of warfarin or stable doses of low molecular weight heparin for > 2 weeks at time of first dose. International normalized ratio should be monitored as clinically indicated per investigator's discretion.

Anti-hypertensives are allowed as concomitant medications; however, because transient hypotension has previously occurred during infusions of IMCgp100 and monoclonal antibodies, [REDACTED]

[REDACTED]

